### 5.4. Procedures to Identify and Characterize High and Low Performing and Sustaining Sites (Aim 3)

We will identify high and low performing sites in both study arms based on SNaP fidelity and

ART uptake targets for PWID clients. We will assess these characteristics qualitatively and quantitatively.

To assess characteristics of high and low performing sites in depth, we will conduct qualitative interviews with:

- HIV-infected PWID, including those that received SNaP and those that declined,
- systems navigators and psychosocial counselors, clinic staff, and clinic directors in both SA and TA arms.
- Health providers and/or adherence counselors at HIV outpatient clinics near these test sites in both SA and TA arms

We will also assess the characteristics of high and low performing sites based on quantitative characteristics derived from the implementation outcomes, test site demographics, and test site context.

To assess characteristics of high and low sustaining sites in depth, we will conduct qualitative interviews with:

- Systems navigators and psychosocial counselors, clinic staff, and clinic directors in both SA and TA arms.

We will also assess the characteristics of high and low sustaining sites based on quantitative characteristics derived from the implementation outcomes, test site demographics, and test site context.

**Our *a priori* definition of successful implementation at 24 months is:**

- A site with a fidelity score of 136 (see Section 7.2) and 70% ART uptake among its newly diagnosed or previously diagnosed and not currently on ART PWID clients.

The fidelity score and ART uptake are based on the Vietnam site's experience in HPTN 074. In the SNaP arm of HPTN 074, 72% of PWID were using ART at 12 months; in Vietnam, 88% of PWID were using ART at 12 months. Based on these results, 70% is a reasonable target for this implementation trial. We will consider any person lost to follow up as having failed ART use and not virally suppressed.

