***The secondary objective of this study is:***

**1) To explore the key characteristics of HIV testing sites and clinics that successfully or unsuccessfully implement SNaP for each study arm. (Aim 3)**

We will use qualitative and quantitative site-level data collected at baseline and study completion to explore critical site characteristics, such as test site size, readiness to change, or implementation climate, of high and low performing sites. Test site-level success will be defined based on a high SNaP fidelity score and ART uptake exceeding 70% in newly diagnosed or previously diagnosed and not currently on ART HIV-infected PWID. We will also assess sustainment of the SNaP intervention at 6-10 months post-completion of 24 months at a given site.

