#### **5.4.1 High and Low Performing and Sustaining Sites Data Collection:**

In-depth interviews - PWID at high and low performing sites: We will conduct six semi-structured in-depth interviews (IDIs) with PWID in each of three sites of the following four site performance types (12 test sites; 72 interviews): 1) SA low performers; 2) SA high performers; 3) TA low performers; and 4) TA high performers. Three PWID will have participated in SNaP and three PWID will have declined SNaP. We will ask participants about barriers and facilitators to uptake of ART and MAT and ART adherence, attitudes and experiences in the HIV test site, with test site staff, and if appropriate, with navigators and counselors.

In-depth interviews - navigators and counselors, clinic staff, and clinic directors: In these same 12 test sites, we will conduct semi-structured IDIs with navigators/counselors (n=12-24), site staff (n=12), site directors (n=12) and HIV providers (n=12) to inform the context and processes that may underlie SNaP success and failures (total n=48-60, depending on the number of navigators and counselors at each site). Topics will include PWID-related stigma; attitudes toward and experience with SNaP, SA, and TA

implementation packages; competing site priorities; perceptions of rewards and leadership support around SNaP; perceptions of effectiveness of SNaP, SA and TA; availability of technical assistance; beliefs around sustainability of SNaP at their test site; collaboration between HIV test sites and HIV outpatient clinics.

Quantitative characterization of high and low performing clinics: We will use the implementation test site context scales for readiness to change, implementation leadership, and implementation climate to characterize each clinic before and after implementation of SNaP. We will also characterize the test sites in terms of overall size (number of HIV tests performed), PWID size (number of HIV tests performed who are PWID), PWID proportion (number of PWID over total tests performed), staff information and current support from NGOs Clinic and PWID characteristics will be assessed before and after implementation.

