## 8. STATISTICAL CONSIDERATIONS

### 8.1. Power and Sample Size Considerations

#### 8.1.1 *Implementation Outcomes Sample Size Calculations*

The **primary implementation outcome is fidelity**, based on an index with a score ranging from 0-200 (see Section 7.2). The **unit of analysis is test site** (n=42 test sites total, 21 per arm).

In HPTN 074, the Vietnam site achieved 86%-88% completion of navigation and counseling sessions in the protocol-specified window, and in our counseling studies we consistently achieve 90-95% quality scores on supervisor-rated counseling sessions. **This track record suggests a “best case” upper bound to the fidelity score of ~150** [(100\*0.85 navigation sessions completed \* 0.9 quality) + (100\*0.85 counseling sessions completed \* 0.9 quality) = 76.5+76.5 = 153].

**We expect TA to achieve close to this “best case” upper bound, with  $\geq 80\%$  appointment completion and  $\geq 85\%$  quality scores, or a fidelity score of  $\geq 136$  = (100\*0.8\*0.85 + 100\*0.8\*0.85). We expect IM to achieve lower session completion and lower quality.**

*Using two-tailed tests and  $\alpha=0.05$  and assuming a conservatively large standard deviation of 40, 42 sites will give us 80% power to detect a difference between a fidelity score of 136 in the TA arm and 100.5 in the SA arm.*

A score of 100.5 in the TA arm corresponds to 75% session completion and 67% average quality ratings (100\*0.75\*0.67 + 100\*0.75\*0.67 =100.5).

With a more plausible standard deviation of 28, we would have 80% power to detect the difference between a score of 136 in the TA arm and 111 (75% completion,74% quality) in the SA arm. Thus, we have power to detect operationally meaningful differences in session completion and quality scores.

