### **8.2.3 High and Low Performing and Sustaining Site Characterization- Analyses (Aim 3)**

**Aim 3 - Qualitative data analyses:** All qualitative interviews will be audiotaped, transcribed, translated, coded and computerized for analysis using Atlas.ti v.8 software. Analysis will begin as data are collected so that topics for further exploration can be incorporated into ongoing fieldwork. Qualitative data analysis consists of the search for patterns in data and conceptualizing ideas that help explain the presence of those patterns. Textual data analysis will involve five steps: 1) reading for content; 2) deductive and inductive coding; 3) data display to identify emerging themes; 4) data reduction; and 5) interpretation. Memos will be written for each code. Codes will be refined during the process of analysis. Responses of navigators and counselors, test site staff, and test site directors will be compared within and across the staff groups and within and across high and low performing and sustaining sites. For example, we will compare navigator and counselors' attitudes around implementing SNaP, including PWID-related stigma, competing job responsibilities at the site, perceived effectiveness of SNaP, and perceived status/value of being navigators and counselors, by high and low performing sites to understand if and how these attitudes may ultimately affect site performance.

**Aim 3 - Quantitative data analyses:** The site characteristics will be assessed with exploratory analyses to examine associations with high and low performing and sustaining clinics. Site is the unit of analysis. Given the small sample size, we will assess each site measure separately. We will use a generalized linear model with a logit link and binomial error distribution to assess the dichotomous outcome of high or low performance and sustainment. Individual implementation or demographic measures will be included as an explanatory variable, with an indicator variable for study arm, and an interaction term (assessed with  $\alpha=0.10$ ). The interaction term will aid in interpreting whether a specific characteristic modified the effect of the implementation strategy. Two sets of models will be constructed: baseline measures only and change from baseline to evaluation.

**Data triangulation:** IDI and quantitative data will be triangulated to understand SNaP

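### Aim 3 models only a joint pass/fail label over 42 sites, discarding measures already collected, with no fallback if the standard arm has fewer than three high performers

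*Combined protocol and SAP*

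**What the plan says.** Section 5.4 gives the a priori definition of success at 24 months, "A site with a fidelity score of 136 (see Section 7.2) and 70% ART uptake", and Section 7.5 repeats it. Both criteria must be met. Section 2.1 words it slightly differently: "Test site-level success will be defined based on a high SNaP fidelity score and ART uptake exceeding 70"%. Section 5.4 applies the same two measures to sort sites: "We will identify high and low performing sites in both study arms based on SNaP fidelity and" ART uptake targets.

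The label is then used twice.

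- Section 8.2.3 fits a logistic model "to assess the dichotomous outcome of high or low performance and sustainment". Its terms are one site measure, an arm indicator and their interaction (tested at 0.10). The analyses are called exploratory and are limited to one measure per model because of the small sample.
- Section 5.4.1 draws three sites from each of four cells for in-depth interviews: "1) SA low performers; 2) SA high performers; 3) TA low performers; and 4) TA high performers".

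Section 8.1.1 ("n=42 test sites total, 21 per arm") also uses 136 as the TA planning value, for example in "the difference between a score of 136 in the TA arm and 111" for SA at SD 28. Section 8.1.2 uses 70% as the higher-arm ART value in its examples.

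The plan gives no expected number of successful sites, no rule for a cell with fewer than three sites, no method for sparse data, and no explicit class for a site that meets only one criterion.

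**The concern.** Fidelity runs from 0 to 200 and ART uptake is a count out of each site's participants. Reducing both to one joint yes/no outcome treats a site at 135 like a site at 60, and a site that passes one criterion like a site that fails both. With 42 sites and a model that carries an interaction, little information is left.

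The fidelity cut is also the TA planning value, and the ART cut is the higher-arm value in the power example. If the trial finds the differences it was sized for, few SA sites would pass both cuts. The SA high-performer cell could then be short, and the interaction models might have no finite estimate. Aim 3 is the secondary objective, and Section 2.1 asks for an answer in each arm.

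**Working it through.** **1. The plan's own power figures.** Section 8.1.1 gives 21 sites per arm, alpha 0.05 ("Using two-tailed tests"), and TA 136 against SA 100.5 (SD 40) or 111 (SD 28). For a two-sample t test on 40 df, the noncentrality is difference / (SD × √(2/21)).

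- SD 40: 35.5 / (40 × 0.3086) = 2.88, power 80.1%.
- SD 28: 25 / (28 × 0.3086) = 2.89, power 80.6%.

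The stated 80% is reproduced. For ART uptake (Section 8.1.2, mean cluster size 148), the design effect 1 + 147 × ICC is 8.35 at ICC 0.05 and 2.47 at ICC 0.01. With 3,100 per arm divided by the design effect, power is 81.6% for 70% vs 60% and 89.2% for 70% vs 64%. Both agree with the stated figure of more than 80%.

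**2. Chance that an SA site passes each cut**, with site values taken as normal and the cuts read as at least 136 and at least 70%.

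- Fidelity: (136 − 111)/28 = 0.893, so 18.6%; (136 − 100.5)/40 = 0.8875, so 18.7%.
- ART uptake: site SD = √[ICC·p(1−p) + (1−ICC)·p(1−p)/148].
  - p = 0.60, ICC 0.05: √(0.0120 + 0.00154) = 0.116; 0.10/0.116 = 0.86, so 19.5%.
  - p = 0.64, ICC 0.01: √(0.00230 + 0.00154) = 0.062; 0.06/0.062 = 0.97, so 16.7%.

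A TA site placed exactly at 136 and 70% passes each cut with probability 50%.

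**3. Both cuts together.** The documents do not give the site-level correlation r between fidelity and ART uptake, so it is varied. The joint probability is bivariate normal, and the count out of 21 is binomial. At r = 0, for example, 0.186 × 0.167 = 0.031, and 21 × 0.031 = 0.65. Ranges cover both SD scenarios and both ICCs.

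| r | SA site passes both | Expected SA successes of 21 | P(at least 3 SA) | Expected TA successes |
|---|---|---|---|---|
| 0 | 3.1–3.7% | 0.65–0.77 | 3–4% | 5.3 |
| 0.3 | 5.4–6.2% | 1.1–1.3 | 10–14% | 6.3 |
| 0.5 | 7.3–8.2% | 1.5–1.7 | 19–24% | 7.0 |
| 0.8 | 11.0–12.2% | 2.3–2.6 | 41–48% | 8.4 |
| 1 | 16.7–18.7% | 3.5–3.9 | 70–78% | 10.5 |

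**4. If SA does better than the planning values.**

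- SA at 125 (SD 28) and 67% (ICC 0.05): 2.9–7.3 expected successes and P(at least 3) of 56–99% for r from 0 to 1 (56–95% for r up to 0.8).
- SA fidelity 100.5 (SD 40), with ART uptake at the 88% that Section 5.4 reports for Vietnam in the earlier trial: 3.9 expected, P(at least 3) 78%.
- SA equal to TA: 5.3–10.5 expected, P(at least 3) at least 92%.

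**5. The interaction model.** With arm and interaction included, the logistic model amounts to a separate curve in each arm. If either arm has no successes, or the characteristic separates successes from failures perfectly, the interaction has no finite estimate. Under the planning differences, total successes over 42 sites are about 6–11 for r from 0 to 0.8, or 2.0–3.6 per slope term (three slopes). In simulation with a characteristic correlated 0.4 with performance, the model was inestimable in roughly 11–39% of trials at r 0.3–0.8. With equal arms this was 4% or less.

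**6. Power lost by the label.** The 0.4 correlation is an assumption. For the fidelity score, adjusting for arm, Fisher's approximation gives atanh(0.4) × √(42 − 3 − 1) = 0.424 × 6.16 = 2.61; 2.61 − 1.96 = 0.65, power about 74%. Simulation gives 72–77%. For the binary label in the same simulated trials, power is roughly 30–51% under the planning differences and 56–68% with equal arms. Wald tests sit towards the lower end of these ranges and likelihood-ratio tests towards the upper end.

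**The case against.** The strongest reply is that the SA values in Sections 8.1.1 and 8.1.2 are differences the trial could detect, not forecasts. Section 8.1.1 says only that the standard arm should do worse, and the ART figures are examples. A reader might infer that the plan leaves too few successful SA sites outright. The documents do not support that: step 4 shows the cell is likely to fill if SA is close to TA, or if ART uptake is near its earlier Vietnam level. This part of the objection stands, so the sampling problem is conditional.

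A reader might also infer that the cuts equal TA's expected means. For fidelity, 136 is a floor for TA (stated as at least 136). For ART uptake, 70% is justified in Section 5.4 as a reasonable target after 72% overall and 88% in Vietnam, and no expected TA mean is stated.

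The conceptual framework in Section 1.3 has high fidelity leading to better ART uptake, which implies a positive r and makes the worst rows of the table less likely. Aim 3 is exploratory, its models are held to one measure each, and it also rests on 72 PWID interviews and 48–60 staff and provider interviews. The sustainment sampling uses PRESS scores, not these cuts.

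These replies lower the stakes. They do not answer the power loss, which remains when the arms are equal, or the missing fallback.

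**Conclusion.** The point holds in two parts.

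- **Unconditional:** modelling only the joint label wastes information already collected. For a characteristic correlated 0.4 with performance, power falls from about 72–77% to roughly 30–51% under the planning differences, or 56–68% with equal arms.
- **Conditional:** if SA trails TA by the differences the trial was sized to detect, about 0.65–2.6 SA sites succeed, the three-site SA high-performer cell fills with probability 3–48%, and the interaction model is inestimable in roughly 11–39% of trials at r 0.3–0.8. The plan has no fallback for this case.

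The figures assume normal site distributions, an average cluster of 148 (actual sizes range from 7 to 764, so uptake at small sites is noisier), r from 0 to 0.8, and the chosen 0.4 correlation. The power comparison is for the main effect of a characteristic; no interaction power was calculated for the continuous model. This is a worthwhile, inexpensive improvement to a secondary, exploratory aim. It does not affect the primary analyses.

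**What to change.** **Section 8.2.3.** Make two models the main Aim 3 quantitative analyses: the site fidelity score (linear), and site ART uptake (binomial counts per site, allowing for overdispersion). Each carries the characteristic, arm and interaction. Keep the 136/70% label and its logistic model as a descriptive or supplementary analysis, fitted with a sparse-data method such as Firth penalised logistic regression.

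**Section 5.4.1.** Keep the absolute definition, since Section 2.1 asks about success against a fixed standard. Add that a cell with fewer than three sites will be filled by ranking sites within arm on a pre-named measure, for example the mean of the standardised fidelity and ART uptake values. Report such sites as relative, not absolute, performers.

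**Cost.** No new data are needed. There are two exploratory outcomes instead of one, hence more tests to interpret. The Section 5.4.1 change is a small protocol amendment that needs ethics approval under Section 12.4.

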#### **5.4.1 High and Low Performing and Sustaining Sites Data Collection:**

In-depth interviews - PWID at high and low performing sites: We will conduct six semi-structured in-depth interviews (IDIs) with PWID in each of three sites of the following four site performance types (12 test sites; 72 interviews): 1) SA low performers; 2) SA high performers; 3) TA low performers; and 4) TA high performers. Three PWID will have participated in SNaP and three PWID will have declined SNaP. We will ask participants about barriers and facilitators to uptake of ART and MAT and ART adherence, attitudes and experiences in the HIV test site, with test site staff, and if appropriate, with navigators and counselors.

In-depth interviews - navigators and counselors, clinic staff, and clinic directors: In these same 12 test sites, we will conduct semi-structured IDIs with navigators/counselors (n=12-24), site staff (n=12), site directors (n=12) and HIV providers (n=12) to inform the context and processes that may underlie SNaP success and failures (total n=48-60, depending on the number of navigators and counselors at each site). Topics will include PWID-related stigma; attitudes toward and experience with SNaP, SA, and TA

implementation packages; competing site priorities; perceptions of rewards and leadership support around SNaP; perceptions of effectiveness of SNaP, SA and TA; availability of technical assistance; beliefs around sustainability of SNaP at their test site; collaboration between HIV test sites and HIV outpatient clinics.

Quantitative characterization of high and low performing clinics: We will use the implementation test site context scales for readiness to change, implementation leadership, and implementation climate to characterize each clinic before and after implementation of SNaP. We will also characterize the test sites in terms of overall size (number of HIV tests performed), PWID size (number of HIV tests performed who are PWID), PWID proportion (number of PWID over total tests performed), staff information and current support from NGOs Clinic and PWID characteristics will be assessed before and after implementation.

Sustainment survey: We will administer the 3-question Provider REport of Sustainment Scale (PRESS) scale to site staff (including counselors and navigators) who were involved with the delivery of SNaP 6-10 months following the completion of the SNaP activities at each site. The purpose of the scale will be to assess the sustainment of the SNaP intervention at each of the sites, as well as characteristics of high and low sustaining sites. Study staff will contact site staff at the 42 HIV test sites that were involved in the SNaP study to invite them to participate in the survey. About 252 clinic staff (6 per site) will participate in the survey. Clinic staff who are interested in participating will be emailed electronic consents via a Qualtrics database to read and sign (if they choose to participate in the survey). They will then complete the fully self-administered survey on Qualtrics. The survey should take no more than 5 minutes to complete.

Sustainment in-depth interviews: We will conduct in-depth interviews with clinic navigators/counselors (n=12) and site staff or site directors (n=24) from a sub-sample of 12 of the SNaP scale-up sites at 6-month post-endline. Based on their scores on the PRESS, we will randomly select 6 “high sustainer” and 6 “low sustainer” clinics for these interviews. The purpose of these interviews is to understand how SNaP and SNaP implementation strategy adaptations influence normalization and sustainment of the SNaP intervention into HIV testing clinics after the removal of external study support. SNaP study staff will contact clinic navigators, site staff, and site directors and will invite them to participate in the interviews. All interviews will be conducted over Zoom in Vietnamese by bilingual Vietnamese research assistants trained in qualitative interviewing. Participants will provide informed consent before being interviewed. The interviews are expected to last approximately one hour. All interviews will be audio-recorded, transcribed verbatim, and translated to English.

## 5.5. Participant Study Procedures

Pre-implementation assessment of site context will be conducted among site directors and site staff. After implementation of the SNaP intervention at test sites (Time 0), post-implementation assessments will occur to evaluate implementation and effectiveness study outcomes.

### **PWID Data**

**PWID enrollment:** All PWID who are confirmed HIV-infected will be given a brief consent form during post-test counseling. This consent will address permission to: 1) extract ART uptake from medical records at local ART clinics and 2) extract MAT uptake from medical records at MAT clinics. Note that consent for SNaP will not be explicitly requested, as it will be considered a routine clinical activity at that site upon trial initiation.

**ART and MAT uptake data:** To initiate ART, all persons in Vietnam must present a confirmation of diagnosis to the ART clinic. Using participants' study masked ID (MID), we will then review the medical record at ART clinics to confirm ART initiation. A similar process will be used for MAT uptake data. **These data will be extracted semi-annually.**

**Viral suppression and interview data:** During months 0-6 and 12-18 after implementation in each test site, a random sample of PWID will be identified for participation in the subsample cohort. These PWID will have an additional consent to allow re-contact and to obtain locator information, including a family member. A few days after diagnosis, the PWID subsample cohort will undergo a brief demographic, behavioral, mental health, and costing questionnaire, administered through the phone by a test site staff member trained and compensated to collect these data.

To enhance retention, the subsample cohort of 1500 PWID will be re-contacted every 3-4 months to maintain contact. If contact with the PWID cannot be established, the family member will be contacted in an attempt to update the locator information. Trained study staff (including training in confidentiality) will attempt to contact family members by phone. If after several attempts the family members are not reached by phone, our trained study staff will attempt to visit the home. (See also **Section 9.6.1.**)

At 12 months post-implementation at a test site, the PWID group enrolled at 0-6 months will be contacted to return to the test site, where a dried blood spot specimen will be collected for viral load testing. A brief questionnaire will also be administered through the phone. The questionnaire will address PWID's perceptions of SNaP and factors that may affect uptake of ART and MAT, including sociodemographic characteristics, injecting behaviors, and costs (costing questionnaire will be administered to only a smaller subset of the 1500 PWID subsample cohort). The PWID will be given an incentive for participation in the subsample cohort.

At 18 months post-implementation, this process will be repeated with PWID group enrolled at 0-12 months. The costing questionnaire will only be administered at this follow-up to only a smaller subset of the 1500 subsample cohort enrolled at 7-12 months.

At 24 months post-implementation, this process will be repeated with PWID group enrolled at 0-18 month. The costing questionnaire will only be administered at this follow-up to a only a smaller subset of the 1500 subsample cohort enrolled at 13-18 months. With this approach, all PWID in the subsample cohort will be assessed for viral suppression 6-12 months after diagnosis (n=1200) (see Section 3.5.1 for explanation of n=1200); the 0-6 month group will have the 12 18, and 24 month assessments and the 13-18 month group will have the 24 month assessment (**Figure 1**).

**Routine HIV Testing Data:** Each test site routinely maintains a log of persons tested for HIV, including associated risk behaviors, such as injection drug use and sexual behavior. These data will be de-identified and used to provide the denominator for the total number of PWID diagnosed with HIV infection.

